18. STUDY ENDPOINT CRITERIA

18.1. Patient Completion of Study

If a study patient has completed the final visit (Visit 7) of the study, he/she is considered to have completed the study.

18.2. Patient Discontinuation

Each study patient may voluntarily discontinue the study at any time they choose. Study patients who cannot complete the study for administrative reasons (e.g., non-compliance, failure to meet visit schedule, etc.) will be discontinued from the study. Study patients discontinued during the enrollment phase (prior to surgery) of the study will be replaced.

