8. STUDY DESIGN

8.1. Study Design

This study is a single site, single-masked, randomized, prospective, contralateral eye study of the efficiency of the Active Sentry handpiece at low IOP compared with the Ozil at high IOP. Subjects will be assessed pre-operatively, operatively and at 1 day and 1 week post-operatively. Clinical evaluations will include measurement of visual acuity and central corneal thickness (CCT).

The primary outcome measure will be the total aspiration time between groups on day of surgery.

Secondary outcome measures are as follows:

- Total fluid volume between groups on day of surgery.
- Total phaco time between groups on day of surgery.
- Total case time between groups on day of surgery.
- Aspiration time during phaco between groups on day of surgery.
- Central corneal thickness (CCT) between groups at postoperative day 1 and week 1.

Exploratory outcome measures are as follows:

- Cumulative dissipated energy between groups on day of surgery.

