10. ANALYSIS PLAN

10.1. Analysis Data Sets

All subjects who are enrolled in the study will be evaluated for safety. Efficacy analyses will be performed based on data from those eyes where uncomplicated cataract surgery was completed.

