10.2. Statistical Methodology

A summary of the data will be prepared for all measurement time points.

For variables measured on a continuous scale, these summaries will include the sample size, as well as the mean, standard deviation, median, minimum, and maximum. For variables measured on a categorical scale, summaries will provide the number and percentage of subjects in each category. These summaries will be provided for all eyes completing the study.

The difference in the aspiration time between groups will be used to test the non-inferiority hypothesis. If the upper boundary of the 95th confidence interval is not greater than 23, non-inferiority will be claimed. In the event that non-inferiority is demonstrated, then a test of superiority will be performed.

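### Outcomes fixed at surgery are tied to post-operative attendance: a missed first-eye visit can forfeit the second eye's aspiration time, and the aspiration-time summary and the non-inferiority test use different populations

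*Combined protocol and SAP*

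**What the plan says.** - **Outcome timing.** Section 8.1: "The primary outcome measure will be the total aspiration time between groups on day of surgery". Table 15.1 places aspiration time at Visits 2 and 2a only. Among the secondary outcomes, only central corneal thickness (CCT) depends on the post-operative visits.
- **Visit windows.** Table 9.2-1 allows days 1 to 2 for the Day 1 visit and day 7 ± 3 for the Week 1 visit, for each eye. It states no interval between the two operations.
- **Discontinuation.** Section 18.2: "Study patients who cannot complete the study for administrative reasons (e.g., non-compliance, failure to meet visit schedule, etc.) will be discontinued from the study".
- **Replacement.** Section 18.2 continues: "Study patients discontinued during the enrollment phase (prior to surgery) of the study will be replaced". Nothing provides for replacement after the first operation.
- **Completion.** Section 18.1: "If a study patient has completed the final visit (Visit 7) of the study, he/she is considered to have completed the study". Section 9.2.5 identifies Visit 7 as the second-eye Week 1 visit (4a in the tables).
- **Efficacy population.** Section 10.1: "Efficacy analyses will be performed based on data from those eyes where uncomplicated cataract surgery was completed".
- **Descriptive summaries.** Section 10.2: "These summaries will be provided for all eyes completing the study".
- **Primary test.** Section 10.2, in a separate paragraph: "The difference in the aspiration time between groups will be used to test the non-inferiority hypothesis".

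**The concern.** Attendance after surgery has no bearing on a measurement already taken in the operating room, yet it enters the plan in two places.

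The first is data collection. In a contralateral design a patient gives a complete comparison only after both operations. An administrative discontinuation between them leaves one handpiece unobserved in that patient, for a reason that concerns only the follow-up measures.

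The second is reporting. If the table of means and SDs covers study completers while the interval covers all eyes with uncomplicated surgery, the reader cannot reconcile the two for the primary variable.

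At stake are some avoidable loss of precision and an inconsistency in the report. The non-inferiority conclusion itself is not in question.

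**Working it through.** **1. The plan's own sample size.** Inputs from section 11: SD 36.8 s, true difference 0, margin 23 s, power 80%, level 5%. For two independent groups, n = 2 × SD² × (z₁ + z₂)² / margin² = 2 × 36.8² × (1.645 + 0.842)² / 23² = 31.7, which rounds up to 32 per group. This matches the plan and shows that it used a one-sided 5% level without pairing. A one-sided 2.5% level would give 41. Recruiting 35 leaves 35 − 32 = 3 spare pairs (3/35 = 8.6%).

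**2. What a missed visit does, by timing.**

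| Visit missed | Primary test (10.1) | Descriptive summary (10.2 with 18.1) |
|---|---|---|
| Visit 3, or Visit 4 if it precedes Visit 2a, followed by discontinuation under 18.2 | Second-eye value never collected; no replacement | Patient is not a completer |
| Visit 4a, after two uncomplicated operations | Both eyes kept | One or both eyes can be left out |

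In the second row the number of eyes left out is unclear, because 10.2 speaks of eyes and 18.1 defines completion for patients. Section 18.3 adds to the mismatch by counting terminated patients as having completed.

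**3. Upper bound on lost pairs.** Assume a miss probability m at each of Visits 3 and 4, independent, with both visits before Visit 2a and every miss leading to discontinuation. Then p = 1 − (1 − m)² and the expected loss is 35p.

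| m (assumed) | p | Pairs lost of 35 |
|---|---|---|
| 2% | 0.0396 | 1.4 |
| 5% | 0.0975 | 3.4 |
| 10% | 0.190 | 6.7 |

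If only half the misses lead to discontinuation, replace m by m/2. Then p = 0.0199, 0.0494 or 0.0975, and the probability that a Binomial(35, p) count exceeds the 3 spare pairs is 0.5%, 9% or 45%. If every miss counts but only Visit 3 precedes the second operation, the expected loss is 35m = 0.7, 1.75 or 3.5 pairs.

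**4. Power on the plan's method.** Power = Φ(23 / (36.8 × √(2/n)) − 1.645).

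| Pairs left | Power |
|---|---|
| 35 | 83.4% |
| 32 | 80.4% |
| 31 | 79.3% |
| 30 | 78.1% |
| 28 | 75.6% |

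Each lost pair costs about 1 to 1.3 points over this range. If the 95% interval in 10.2 is two-sided (the plan does not say), the corresponding figures are 74.4% at 35 pairs and 70.5% at 32. That is a separate matter, and the cost per lost pair is similar.

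**The case against.** The strongest reply is that section 10.1 already protects the primary test. It imposes no attendance condition, and the completer restriction in 10.2 belongs to the descriptive summaries, not to the non-inferiority paragraph. This stands. A reader might infer from 18.2 and 10.2 together that any missed post-operative visit removes a pair from the primary comparison. The documents do not support that: once both operations are finished and uncomplicated, both eyes stay in.

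Three further replies stand in part.

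- **Visit order.** The tables group visits by eye and give no interval between surgeries. If the second operation follows within about a week, Visit 4 may come after it, and that part of the route closes. The Visit 3 part remains unless the second operation comes sooner still.
- **Reading of 18.2.** It covers patients who cannot complete, with visit timing as an example, so a patient who is merely late is not clearly caught. Section 9.5 makes discontinuation permissive and does not list a missed visit, although its list includes protocol violations and other reasons. The loss figures are therefore ceilings. With every miss counted, the chance of exceeding the 3 spare pairs would be 5%, 45% or 92%, but those are not forecasts.
- **Pairing.** The plan does not name a paired test, so a lost second eye need not remove the first eye from the analysis. The power table, which removes both, is again cautious.

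A reader might also infer that the lost pairs would bias the comparison, because attendance could reflect how the first operation went. Nothing in the documents establishes that link.

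None of this recovers a second-eye value that was never collected, or reconciles the populations in 10.1 and 10.2.

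**Conclusion.** The point holds in a limited form, and its severity is minor.

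- **Population mismatch.** It follows from the text with no assumption about rates. A patient with two uncomplicated operations who misses Visit 4a is in the non-inferiority test, but one or both eyes can be missing from the aspiration-time summary.
- **Loss of second-eye data.** It is conditional on a missed first-eye visit, on 18.2 being applied, and on this happening before the second operation. The upper bound is 1.4 to 6.7 of 35 pairs for assumed miss rates of 2% to 10% per visit. Even near the top of that range power falls by about 8 points (83.4% at 35 pairs to 75.6% at 28), and up to 3 lost pairs are already covered by recruitment.

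**What to change.** **Section 10.2.** Replace the completer restriction with the section 10.1 population, summarising all eyes in it that have data at the time point concerned. The aspiration-time summary and the non-inferiority interval then describe the same eyes.

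**Section 18.2.** Remove visit timing from the examples of administrative discontinuation. Record a missed or out-of-window post-operative visit as a protocol deviation, flag that visit's data as missing or out of window, and still collect adverse events at the next contact. Adverse events are monitored at these visits, so the new wording should not imply that only CCT, slit-lamp and visual acuity data are affected.

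Discontinuation for safety at the investigator's judgment (9.5) and termination (18.3) stay as written.

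**Cost.** Two short wording changes and no added visits. Some CCT values will be missing or out of window and will need to be identified as such.

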18.3. Patient Termination

A study patient will be terminated if the study patient develops any severe adverse event that may be related to the study. A study patient will receive appropriate treatment at the discretion of the investigator. Notification of termination will be clearly documented. These study patients are considered to have completed the study and will not be replaced.

18.4. Study Termination

The investigator with appropriate notification may terminate the study. If, after clinical observations, the investigator feels that it may be unwise to continue the study, he may stop the study.

18.5. Study Completion

The study will be complete when all enrolled patients have completed Visit 7 or have been terminated from the study.

19. SUMMARY OF RISKS AND BENEFITS

19.1. Summary of risks

The risks with this study are similar to those for any patient receiving sequential bilateral cataract surgery. There is no increased risk associated with the proposed study.

